A.3. Frail Veterans frequently undergo major surgery with dramatically increased morbidity and mortality. Some form of frailty is present in half of all Veterans undergoing colorectal and cardiac surgery,⁵ and one third of the US population is expected to undergo a major surgical procedure within the last year of life.⁴⁵ Some frail patients clearly benefit from surgery through improved symptom management and extended life. However, the high rate of surgical morbidity and mortality among the frail suggests that for many, surgery confers significant burdens for patients, families, and society at large.⁴⁻⁹ For example, compared to robust patients, frail surgical patients are less likely to be discharged to home,⁸ more likely to be readmitted within 30 days,^{5,9} and have substantially increased rates of perioperative mortality and complications.^{4,6,7,9} In fact, our preliminary analysis demonstrates similar patterns across 1,632 major abdominal operations performed at VAPHS from 2010 to 2014 where 192 (11.8%) Veterans with differing degrees of frailty suffered dramatically increased mortality, morbidity and length of stay. Even in the mildly frail, 30-day postoperative mortality was 10 times greater than among the robust (4% vs. 0.4%, $p < .001$), and increased dramatically with increasing frailty. However, little is known about how to improve the surgical outcomes of frail patients.

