B.2. Development, validation, and implementation of the Risk Analysis Index (RAI) of frailty. None of the existing tools for measuring frailty have proved suitable for widespread, prospective clinical screening. To fill this gap, Drs. [name] and [name] developed, validated and refined the RAI that can be calculated retrospectively from VA Surgical Quality Improvement Program (VASQIP) data or prospectively from a 2-minute 14-item survey. Both versions of the RAI yield a continuous score that captures a full range of frailty from robust (0-15) to mild (16-25), moderate (26-35) and severe frailty (≥ 36). From July 2011 to September 2015, they used the 14-item survey to assess frailty in a consecutive cohort of 6,905 patients scheduled for surgery at the Omaha VAMC. In this cohort, the RAI has strong predictive power for 6-month mortality (c-statistic=0.772).⁶⁶ At a cutoff of ≥ 16 , the RAI survey classified 12.5% of the cohort as frail with a sensitivity of 0.50 and specificity of 0.90. By linking this cohort to VASQIP data, they compared the RAI to the previously validated, retrospectively calculated modified Frailty Index (mFI)⁶⁷ in a sub-sample of 1,024 patients where the RAI survey (c=.797) performed on par with the mFI (c=.811), thus establishing preliminary convergent validity with the advantage of prospective assessment that can inform real-time clinical decisions. Based on these data, the RAI questionnaire was implemented as standard of care for pre-surgical risk stratification at the Omaha, Pittsburgh, Atlanta, Nashville and Phoenix VAMCs.

B.3. Effective implementation of exercise training programs in frail heart failure patients and recruiting subjects into training trials. [name] was Site PI for both the NHLBI aerobic training trial HF-ACTION⁶⁸ and the NCCAM Tai Chi Mind-Body Movement Therapy for Patients with Chronic Heart Failure.⁶⁹ He is skilled in the prehabilitation techniques planned for this investigation, reliably achieving both training effects and endpoints. For example, in a trial of older female patients, those randomized to a strength training program similar to that proposed here had significantly increased strength ($43.4 \pm 8.8\%$ vs. $-1.7 \pm 2.8\%$ in controls, $p= 0.001$) and endurance ($299 \pm 66\%$ vs. $1 \pm 3\%$, $p= 0.001$).⁷⁰ [name] RR&D I01 is currently randomizing 200 heart failure patients to regimens similar to those proposed here that focus on strength training and IMT.

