*** Research Procedures/Interventions:**

D.1. Overview. We will conduct a randomized pilot study of a prehabilitation intervention in a consecutive sample of up to 50 frail patients scheduled for elective major abdominal surgery at the VAPHS. Participants will be recruited from the mandatory preoperative IMPACT clinic where all patients are routinely screened for frailty. Frail patients agreeing to participate will be randomized 1:1 to (a) standard preoperative optimization by the IMPACT clinic or (b) prehabilitation + standard IMPACT optimization. The prehabilitation intervention will deploy existing cardiac rehabilitation resources to provide (a) strength and balance training, (b) respiratory muscle training, and (c) nutritional coaching and supplementation. Using physical performance tests, biomarkers, chart review, survey instruments, and patient logs, we will assess the feasibility of the recruitment, randomization, retention and assessment procedures, compensating patients for their time.

D.4. Eligibility criteria. We will include all patients with RAI>16 scheduled for major abdominal surgery on the general or urological surgery services. Major surgery is defined according to VASQIP criteria to include cases requiring general, epidural, or spinal anesthesia.

For general and urological surgery, it includes 270 standard, 356 intermediate, and 34 complex procedures, but excludes 291 low risk, "minor" surgical procedures with limited morbidity (e.g., abscess drainage, lipomas, or hemorrhoids). From these major surgeries, we will include those abdominal procedures that deliberately violate the peritoneal or retroperitoneal spaces. For example, from the general surgery service we will include all bowel resections, biliary procedures, and abdominal wall reconstructions, but exclude open, anterior inguinal hernia repair. The list of included CPT codes (see Appendix) represents 56% and 35% of the general and urological surgery volume at VAPHS, respectively (Table 2 below). Given the burden of comorbidity among the frail, we anticipate that many eligible Veterans will have concurrent cognitive impairment or dependent living situations. These limitations need not preclude inclusion so long as the patient can provide first-person informed consent and participate in the prehabilitation regimen described below (D.6). No other exclusions are planned.

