D.5. Randomization procedures and their rationale. Some patients may be reluctant to accept the possibility of randomization to control conditions, and if so, recruitment rates of a randomized trial would be diminished. We will therefore use the randomization feature in REDCap to randomize participants in a 1:1 ratio. As each patient enrolls, REDCap will assign the patient to intervention or control conditions as specified by a fixed allocation table. If patients refuse participation based on the risk of randomization, we will note this fact, but offer the opportunity to participate in the preferred arm (intervention or control). This approach will permit accurate estimates of randomization while accruing the largest possible sample size.

D.6. Prehabilitation Procedures.

(a) Overview. Prehabilitation will include hospital- and home-based components within an integrated intervention led by [name]. The hospital-based component will occur at the VAPHS Cardiac Rehabilitation facility and focus on supervised strength and balance training. One-hour sessions will be scheduled twice weekly for at least 4, but no more than 6 weeks before the operation. The home-based component will entail walking or seated pedaling on a home exerciser, as well as Respiratory Muscle Training (RMT), both of which are feasible and safe to do in a non-supervised setting. Nutritional supplementation will be linked to the composite training protocol. Compliance will be measured with exercise log books (See Appendix) and pedometers given to each participant. With the consent of the surgeon, operative dates will be scheduled to accommodate prehabilitation.

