person-time where person-time is defined as the amount of time a patient is followed from study start to either the end of study, death or loss to follow-up (whichever occurs first). We will also compute summary statistics (mean, median, standard deviation, range) for length of hospital stay, health-related quality of life, quality of surgical care and recovery to independent living. We will make assessments overall and by treatment group. While our emphasis is to assess feasibility, we will also attempt to assess if differences exist between the intervention and control conditions with regards to these post-operative measures.

D.11. Justification of Pilot sample size. Based on the historical surgical volume at VAPHS, the participating surgical services will treat 54 eligible patients who meet our inclusion criteria during a 7 month recruitment window (Table 3). We are not estimating the effect size between intervention and control conditions. Although there is a tradition of using pilot studies to do so, there is growing consensus that this approach is ill-founded because the small samples result in imprecision that makes power estimates unreliable.²³ Therefore, based on recruitment and retention rates estimated here (Aim 1), we will power our subsequent study based on “minimum clinically meaningful differences” defined for each outcome *a priori*.²⁴

Table 3: Sample Size Estimates	General	Urology	Total
Total Surgical Cases/year	1488	610	2098
VASQIP Eligible Cases/year	748	298	1046
Proportion Abdominal	56.2%	35.3%	$\bar{x}=50.2\%$
Proportion Frail	12.0%	10.3%	$\bar{x}=11.5\%$
Eligible Cases/year	70.9	21.5	92.4
Eligible Cases/7 month recruitment	41.4	12.5	53.9

References:

* Please provide a list of references (Multi-site protocols: You may reference the page numbers in the original protocol):

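### D.10(e) summarises and compares the arms without using baseline RAI, although the protocol presents frailty as a leading predictor of the same outcomes

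*Combined protocol and SAP*

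**What the plan says.** A.3 describes 1,632 major abdominal operations at the site, 192 of them in frail Veterans. Thirty-day mortality was 4% in the mildly frail against 0.4% in the robust, "and increased dramatically with increasing frailty". The Abstract calls frailty a stronger predictor of mortality, morbidity, length of stay and cost than age or comorbidity alone.

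B.2 grades the score from "robust (0-15) to mild (16-25), moderate (26-35) and severe frailty" (36 and above). D.4 sets entry as "We will include all patients with RAI>16" with no upper limit, so all three frail bands can enter. Under D.1, patients are screened for frailty in the clinic from which they are recruited, and Table 1 lists frailty at baseline. RAI is therefore available for everyone before allocation.

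D.5 says that "REDCap will assign the patient to intervention or control conditions as specified by a fixed allocation table", in a 1:1 ratio; it names no stratum or block. Patients who decline because of randomization may still take part in the arm they prefer. The sample is up to 50.

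D.10(e) plans death and complication rates with confidence intervals, and summary statistics for stay, quality of life, quality of care and independent living, overall and by arm. It adds that "we will also attempt to assess if differences exist between the intervention and control conditions". No test, model, covariate or analysis population is named. RAI appears in D.10(d), as an outcome in the Aim 2 models. D.11 states that the between-arm effect size is not being estimated.

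**The concern.** The protocol's case for the trial is that frailty drives surgical outcome. A.4 stresses that the team's earlier mortality result held after controlling for frailty. Here the same factor varies widely among participants, is measured on all of them, and is not used when the arms are set side by side. In a trial of about 50, one arm can easily receive more of the moderately and severely frail. A reader of the by-arm table would then have no means of telling a frailty difference from a treatment difference.

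A second route does not depend on chance. Patients who choose their arm under D.5 may differ systematically in frailty between arms, and D.10(e) does not say whether they are kept out of the by-arm summaries.

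**Working it through.** **Figures in the plan.** 192/1,632 = 11.8% and 4%/0.4% = 10, as A.3 states. No sample-size calculation for an arm comparison exists to reproduce; D.11 rests on recruitment volume.

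**Inputs.** From the documents: at most 50 patients, 1:1, hence 25 per arm if all are randomized; 4% 30-day mortality in mild frailty. Assumed, because the documents do not give them: 20-50% of participants moderately or severely frail; 10-20% mortality in that group; a correlation of RAI with a continuous outcome of 0.2-0.5.

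**1. Chance of imbalance.** With K moderately or severely frail patients among 50 and 25 drawn to one arm, the number in that arm is hypergeometric. A 20-point difference is 5 patients. The difference has the same parity as K, so for even K the smallest qualifying value is 6.

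| K (share) | Smallest qualifying difference | Probability |
|---|---|---|
| 10 (20%) | 6 | 0.074 |
| 15 (30%) | 5 | 0.217 |
| 20 (40%) | 6 | 0.148 |
| 25 (50%) | 5 | 0.258 |

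For mean RAI, the standardized difference has standard error sqrt(2/25) = 0.283. The chance that it reaches 0.3 is 29%, and 0.5 is 8%. If only 18 per arm were randomized, the latter would be 13%.

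**2. Effect on mortality,** treated as a 30-day proportion for simplicity. Shift = imbalance × (mortality in moderate/severe − 0.04).
- K = 15: 5/25 × (0.10 − 0.04) = 1.2 points; 5/25 × (0.20 − 0.04) = 3.2 points.
- K = 20: 6/25 × 0.06 = 1.4 points; 6/25 × 0.16 = 3.8 points.

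Standard error of the crude difference = sqrt(2p(1 − p)/25), where p is overall mortality.
- Lowest case: p = 0.7 × 0.04 + 0.3 × 0.10 = 0.058, giving 6.6 points.
- Highest case: p = 0.6 × 0.04 + 0.4 × 0.20 = 0.104, giving 8.6 points.

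The shift is therefore about 0.2 to 0.45 of a standard error (1.2/6.6 to 3.8/8.6). One death moves an arm by 1/25 = 4 points. Expected deaths in total are 50 × 0.058 = 2.9 to 50 × 0.104 = 5.2.

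**3. Effect on a continuous outcome.** Adjusting for a covariate with correlation r leaves 1 − r² of the variance.
- r = 0.2: 4% of variance removed; standard error falls by 1 − sqrt(0.96) = 2%.
- r = 0.4: 16% removed; standard error falls by 1 − sqrt(0.84) = 8%.

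Given a realised RAI difference of 0.5 SD, the two-sided 5% error of an unadjusted test becomes 6% at r = 0.2, 7% at r = 0.3 and 11% at r = 0.5. With RAI exactly balanced it is 4.5%, 4.0% and 2.4%. Over all randomizations the 5% level is kept.

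**The case against.** The strongest reply is that this is a feasibility pilot. D.11 disclaims effect estimation, randomization is unbiased on average, and the planned confidence intervals already allow for chance allocation. All of that stands, and it limits the weight of the point. It does not remove it: D.10(e) still attempts a comparison, and treatment-specific summaries are a stated part of Aim 3.

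Four stronger readings are tempting, and the documents do not support them.
- A reader might infer from A.3 that complications and stay also rise with degree of frailty. The gradient by degree is stated for 30-day mortality only. For morbidity and stay, A.3 reports an increase in the frail as a group.
- A reader might fear that distorted by-arm rates feed the next trial's sample size. D.11 says that trial will be powered from Aim 1 recruitment and retention rates and from differences fixed in advance.
- A reader might conclude that the allocation table has no frailty strata. D.5 names none, but it does not describe the table's contents.
- A reader might call chance imbalance a bias. It is a conditional problem and a matter of precision.

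It is also fair to say that stratum-weighted risk differences for death would be unstable on about 3 to 5 deaths, and would not match the person-time rates that D.10(e) specifies.

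**Conclusion.** The point holds in modest form. Baseline RAI is on hand for every participant, the protocol treats frailty as strongly prognostic, and D.10(e) sets the arms side by side without it. An imbalance of 20 points or more in moderate or severe frailty has roughly a 7-26% chance at 25 per arm, for an assumed share of 20-50%.

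For mortality, the resulting shift of 1.2 to 3.8 points (assumed 10-20% mortality in moderate/severe frailty) is minor beside a standard error of about 7-9 points. The practical gain lies in length of stay and the continuous scores, and even there it is a 2-8% smaller standard error for an assumed correlation of 0.2-0.4, plus protection in the allocation actually obtained. The documents give no within-frail correlation for these outcomes, so the gain could be smaller. The patients who choose their arm are the less predictable part, because no allocation table balances them.

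**What to change.** In D.10(e):
- Report the baseline RAI distribution by arm, as a continuous score and by the B.2 bands.
- Wherever arms are compared, use randomized patients only. Show those who chose their arm under D.5 separately.
- Adjust length of stay and the continuous scores for baseline RAI as a continuous covariate. Say that this overrides the D.10(a) rule of categorising skewed variables.
- Leave deaths and complications as by-arm rates with confidence intervals, to be read beside the RAI table.
- Label any arm comparison exploratory, which brings D.10(e) into line with D.11.

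The cost is a few sentences and one table, from data already collected.

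Optional, and only if enrolment has not begun: load the REDCap table in two RAI strata (mild; moderate or severe) with permuted blocks. Blocks of 4 cap the imbalance at 2 patients per stratum, and mixed blocks of 4 and 6 at 3. The price is a slightly more predictable next assignment. If the table is already stratified, one sentence in D.5 should say so.

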*** Research Procedures/Interventions:**

D.1. Overview. We will conduct a randomized pilot study of a prehabilitation intervention in a consecutive sample of up to 50 frail patients scheduled for elective major abdominal surgery at the VAPHS. Participants will be recruited from the mandatory preoperative IMPACT clinic where all patients are routinely screened for frailty. Frail patients agreeing to participate will be randomized 1:1 to (a) standard preoperative optimization by the IMPACT clinic or (b) prehabilitation + standard IMPACT optimization. The prehabilitation intervention will deploy existing cardiac rehabilitation resources to provide (a) strength and balance training, (b) respiratory muscle training, and (c) nutritional coaching and supplementation. Using physical performance tests, biomarkers, chart review, survey instruments, and patient logs, we will assess the feasibility of the recruitment, randomization, retention and assessment procedures, compensating patients for their time.

D.4. Eligibility criteria. We will include all patients with RAI>16 scheduled for major abdominal surgery on the general or urological surgery services. Major surgery is defined according to VASQIP criteria to include cases requiring general, epidural, or spinal anesthesia.

For general and urological surgery, it includes 270 standard, 356 intermediate, and 34 complex procedures, but excludes 291 low risk, "minor" surgical procedures with limited morbidity (e.g., abscess drainage, lipomas, or hemorrhoids). From these major surgeries, we will include those abdominal procedures that deliberately violate the peritoneal or retroperitoneal spaces. For example, from the general surgery service we will include all bowel resections, biliary procedures, and abdominal wall reconstructions, but exclude open, anterior inguinal hernia repair. The list of included CPT codes (see Appendix) represents 56% and 35% of the general and urological surgery volume at VAPHS, respectively (Table 2 below). Given the burden of comorbidity among the frail, we anticipate that many eligible Veterans will have concurrent cognitive impairment or dependent living situations. These limitations need not preclude inclusion so long as the patient can provide first-person informed consent and participate in the prehabilitation regimen described below (D.6). No other exclusions are planned.

D.5. Randomization procedures and their rationale. Some patients may be reluctant to accept the possibility of randomization to control conditions, and if so, recruitment rates of a randomized trial would be diminished. We will therefore use the randomization feature in REDCap to randomize participants in a 1:1 ratio. As each patient enrolls, REDCap will assign the patient to intervention or control conditions as specified by a fixed allocation table. If patients refuse participation based on the risk of randomization, we will note this fact, but offer the opportunity to participate in the preferred arm (intervention or control). This approach will permit accurate estimates of randomization while accruing the largest possible sample size.

D.6. Prehabilitation Procedures.

(a) Overview. Prehabilitation will include hospital- and home-based components within an integrated intervention led by [name]. The hospital-based component will occur at the VAPHS Cardiac Rehabilitation facility and focus on supervised strength and balance training. One-hour sessions will be scheduled twice weekly for at least 4, but no more than 6 weeks before the operation. The home-based component will entail walking or seated pedaling on a home exerciser, as well as Respiratory Muscle Training (RMT), both of which are feasible and safe to do in a non-supervised setting. Nutritional supplementation will be linked to the composite training protocol. Compliance will be measured with exercise log books (See Appendix) and pedometers given to each participant. With the consent of the surgeon, operative dates will be scheduled to accommodate prehabilitation.

(b) Hospital-based Training will be scheduled twice weekly and include strength and balance training. All sessions will begin with an assessment of the subject's vital signs and a review of their progress with home-based training. Based on evaluation of the exercise log books and pedometer data, the exercise physiologist will reinforce the goals and techniques of the home-based regimen as needed. After the assessment phase, subjects will complete 5 minutes of warm-up with low-intensity walking or seated pedaling. Seated pedaling can be used to exercise the upper extremities in cases of lower extremity disability. Mode of exercise will depend on patient preference and safety, but the same mode of exercise will be used in both the hospital- and home-based regimens (see below). Subjects will then complete 10 minutes of balance training tailored to each subject's capacities and progressing as tolerated. Regimens will uniformly include elements of static, tandem and one-foot stands, weight shifts, side steps, crossovers, grape vines, backward walking, and stepping over objects. Balance training will be coupled with an additional 10 minutes of transitional movement training to enable and strengthen the proper form of movements required after surgery such as lying-to-sitting and sitting-to-standing. Next, subjects will complete 25 minutes of strength training (2 sets with 8-12 repetitions) focused on a spectrum of antagonist muscles for the core abdominal muscles impacted by surgery, including hip flexors and extensors, obliques, rhomboids, erector spinae, and latissimus dorsi. In addition, to optimize mobility and daily function, we will target other muscle groups in the legs, arms, and hands (quads, hamstrings, calf, biceps, triceps, and hand groups). The hospital-based session will finish with full body stretching and reassessment of vital signs. During each session, the exercise physiologist will use a log book (Appendix) to

record completion of each component along with details about the duration and intensity of the aerobic training, balance, and weight training. Regimens such as this have been shown to be both safe and effective among the frail elderly,⁷⁶ and the improvements in strength and balance will likely facilitate early mobilization after surgery—an intervention shown to improve outcomes after surgery.⁵⁶

(c) Home-based Training: Patients will be coached to complete home-based training at least 2-3 days a week and more as tolerated. Exercise will start with a 5 minute warm-up (i.e., slow paced walking or seated pedaling, consistent with the mode of exercise used in the hospital). The same exercise modality will then extend for an additional 30 minute aerobic training session. This phase will entail efforts at a comfortable speed with increasing duration. We will coach patients to reach 30 minutes of continuous, moderate exertion of 11-13 on the Borg Rating of Perceived Exertion (RPE) scale,⁷⁷ but it is expected that initially many subjects may only tolerate shorter intervals. In that case, 5-10 minute intervals of less intense (slower) walking or pedaling may then be combined with periods of rest, with the goal of repeating and elongating them as tolerated until 30 continuous minutes are achieved. If/when 30 minutes of continuous exercise is achieved (at RPE 11-13), the next step will be to progress the intensity (speed) with short periods of relatively greater speed (RPE 13-15) for 1-2 minutes, and alternate with slower intensity (speed) at RPE 11-13. Patients will record the duration and exertion of training in their log books along with step counts from their pedometer affixed to either the patient's waist (walking) or wrist/ankle (pedaling). Family members or other caregivers can assist patients in completing the log books if needed. After aerobic activity, home-based exercise will continue with 30 minutes of progressive RMT using a Threshold RMT device (Respirronics™). Threshold RMT requires that subjects inspire and exhale through a mouthpiece at a comfortable rate using diaphragmatic breathing techniques. The Threshold IMT device prohibits the subject from inhaling or exhaling until a set negative pressure is achieved and overcome. This is accomplished through the use of weighted plungers or spring-loaded valves. It is inexpensive, convenient, and easy to administer at home. We will set each patient's threshold to 40% of maximal inspiratory and expiratory pressures (MIP & MEP) as measured by the Test of Incremental Respiratory Endurance (TIRE)⁶⁰ device, a breathing assessment tool that links a pneumotachometer to a computer tablet and can be used gauge inspiratory pressures. MIP & MEP are the peak pressures generated by respiratory muscles when patients forcibly inhale or exhale against resistance. It is analogous to a maximum weight lifted in the gym but measures the strength of the diaphragm and accessory breathing muscles. MIP & MEP will be defined as the average of 3 assessment breaths on a TIRE device. MIP & MEP will be measured at the first hospital-based session and bi-weekly thereafter, adjusting the Threshold RMT device to maintain a workload at 40% of MIP & MEP as respiratory muscle conditioning improves. Patients will again record the threshold and number of breaths completed in the 30-minute session in log books. Family members or other caregivers can assist patients in completing the log books if needed. Regimens such as this have been shown to increase MIP (15 cm H₂O, 95% CI 9-21) and halve the risk of postoperative pulmonary complications following abdominal surgery (relative risk 0.48, 95% CI 0.26 to 0.8).⁷⁸

(d) Nutritional Counseling. Malnutrition at hospital admission increases length of stay,⁷⁹ and nutritional supplementation has been shown to enhance both wound healing⁵⁹ and exercise-induced improvements in physical performance.⁵⁸ Based on patient preference and convenience, we will arrange for a standard consult with VAPHS Nutrition Services to coincide either with the initial IMPACT clinic visit or the first scheduled visit to the Cardiac Rehabilitation facility. Staff nutritionists (see letter) will administer the standardized Subjective Global Assessment (SGA) of nutrition (Appendix) to identify nutritional needs and classify the patient as either normal or mildly, moderately or severely malnourished. All patients will receive best practice nutritional counseling focused on lean, high protein foods in preparation for surgery.

Cardiac rehabilitation personnel will be trained to assess and reinforce progress on these dietary practices. In addition, standard of care nutritional supplementation will be prescribed to malnourished patients, including Impact® Advanced Recovery, an immunomodulating formula shown to improve outcomes after major surgery.⁸⁰ Supplements will be delivered to patient's homes. Patients will also record their meals and supplements in log books (Appendix), and cardiac rehab personnel will be trained to monitor and encourage consumption of the supplements as prescribed during the hospital-based coaching sessions. Family members or other caregivers can assist patients in completing the log books if needed. Although the evidence is somewhat equivocal, approaches such as this have been shown to reduce postoperative complications (relative risk 0.67, 95% CI 0.53-0.84).⁸¹

(e) Occupational and Physical Therapy (OT/PT). We will arrange for a standard OT/PT consult to coincide with either the initial IMPACT clinic visit or the first scheduled visit to the Cardiac Rehabilitation facility. Staff therapists (see letter) will perform routine, standardized assessments of the patient's home, environment and mobility, prescribing and supplying indicated durable medical equipment to aid mobility, exercise, and safe transition to independent living at home after the proposed surgery. As per their usual protocol, the PT/OT consult will consult with the Social Work services to adequately assess the home environment and supports in anticipation of postoperative discharge planning.

D.7. Assessment Schedule. As shown in Table 1, research staff will collect baseline data at the time of recruitment regarding demographics, physical performance, and nutrition. We will monitor physical performance, nutrition and compliance every other week during in-hospital prehabilitation and on the day of surgery. Postoperative outcomes will be assessed 30 or 90 days after the surgery. Patient Survey Instruments will be administered either face to face, by telephone or by mail, depending on patient preference. Responses will be entered directly into REDCap using a project utility distinct from the RAI measurement tool. For patients electing surveys by mail, we will send printed copies of the Redcap forms with a self-addressed, stamped envelope for return. Responses on returned surveys will be keyed into Redcap before storing the paper surveys in locked cabinets. Instruments assessing living location, quality of life, quality of surgical care, and decision quality are described in D.8. and in the Appendix. Chart reviews will be completed by the research assistant to determine details of the surgical procedure, including postoperative mortality, length of stay, and major complications. Physical Performance Tests will be administered by the exercise physiologist in the Cardiac Rehabilitation facility, located near the IMPACT clinic, and thus convenient for patients to visit on both the days of recruitment and surgery. Nutrition assessments include serum prealbumin and Body Mass Index (BMI) collected biweekly by hospital phlebotomists, and the 7-point Subjective Global Assessment (SGA-7)²⁸ administered by hospital nutritionists at baseline and again on the day of surgery. Patient Logs will assess patient compliance with the home-based prehabilitation regimen and document progress with aerobic training, IMT and nutritional supplementation. They will be collected weekly and on the day of surgery. *Those randomized to control conditions will not complete the patient logs or the weekly in-hospital assessments, but they will complete all other assessments.*

Assessments will end after the assessment planned for 90 days after the surgery. Ideally, patients will return to the hospital for this final visit to conduct measures of physical performance and nutrition along with the survey instruments. However, if they are unable to make the visit, we will conduct the surveys over the phone.

Table 1: Assessment Schedule

	Baseline	Every other Week In-hospital	Day of surgery	30 Days post-op	90 Days post-op
Demographics					
Age, sex, race, ethnicity, etc	X				
Procedure-related variables	X			X	
Living Location	X		X	X	X
Physical Performance					
SPPB	X	X	X		x
MIP & MEP	X	X	X		x
6 Minute Walk Test	X	X	X		X
Frailty (multiple measures)	X	X	X		x
Nutrition					
Prealbumin (biweekly)	X	X	X		x
BMI	X	X	X		x
Subjective Global Assessment	X		X		x
Compliance					
Patient Logs			X	X	
Outcomes					
Mortality				X	X
Length of Stay				X	
Major Complications (30 day)				X	
Quality of Life	X		X		X
Quality of Surgical Care (Pre)			X		
Quality of Surgical Care (Post)				X	
Measures of Decision Quality	x		x	X	x

Minimizing the Burden of Assessments: Some participants in this study will be concurrently enrolled in a related study of frailty and preoperative palliative care consultation (Pro1840). Some of the outcome assessments planned for Pro1754 are identical to those planned here. When a participant is enrolled in both studies (Pro1840 and Pro1754) the study

coordinators will work together to ensure that participants do not have to complete identical assessments twice. At any given time point when potentially duplicative assessments could occur, study staff will record the participant's singular response to a duplicative question simultaneously into the case report forms (CRFs) of each separate study. This could be accomplished by having a two separate study staff on the phone or in the room as the patient is interviewed. It could also be accomplished by having a single cross-listed staff member (e.g., listed on the staff form of both studies) administer the assessment and record the responses into the separate CRFs of each study at the same sitting. Additionally, some participants may be concurrently enrolled in a minimal risk study (PI [name] MD; Pro1843) that has similar inclusion criteria. However, participation in Pro1843 will not impact the outcomes of this protocol (1754).

D.8. Variables Assessed.

- Age, sex, race, ethnicity and socioeconomic status will be assessed by direct patient survey or chart review.
- Procedure-related variables will include the CPT codes of the initially planned operation as well as the operation actually performed. We will also abstract from the chart the type of anesthesia, the duration of the procedure, and the disposition of the patient at the end of surgery (e.g., discharge v. admission)
- Living Location is the environment where patients are living before and after the index operation (i.e., home, nursing home, etc). It will be assessed by direct patient survey or chart review and followed as an outcome.
- Short Physical Performance Battery (SPPB) is a test of balance, gait, strength, and endurance that combines gait speed, repeated chair stands and balance tests that together take less than 5 minutes to complete. Each of the 3 tests are scored on a scale from 0-4 with a combined score ranging from 0-12 with lower scores indicating worse performance.²⁶ Scores below 8 or 10 are interpreted as poor performance.⁸² The SPPB accurately predicts adverse outcomes such as disability, hospitalization, nursing home admission, frailty and mortality, and is becoming the reference standard in rehabilitation literature.⁸²⁻⁸⁶
- 6 Minute Walk Test is a standard measure of physical performance that measures the total distance traversed in 6 minutes, measured in meters. Clinically significant differences can be quantified in as little as 30 meters. This is an exploratory measure that will only be administered if time allows. As a pilot study, we aim to determine what kinds of assessments are feasible in this group.
- Maximal Inspiratory & Expiratory Pressures (MIP & MEP) are the standard metrics of respiratory muscle strength²⁷ and will be measured using the TIRE device described above (D.6c). It has been shown that changes as small as 15 cm H₂O can significantly reduce postoperative pulmonary complications and length of stay.⁷⁸
- Frailty will be assessed through several measures because no single measure of frailty captures the breadth of the syndrome. In addition to the RAI described above, we will quantify the Hopkins & Edmonton Frail Scales and independently analyze the gait speed and handgrip strength that is part of the Hopkins Frail Scale. We recently developed a streamlined approach to measuring all of these metrics simultaneously in a parsimonious exercise that takes <5 minutes to administer.⁸⁷
 - Hopkins Frail Scale encompasses slowness, weakness, weight loss, low physical activity, and exhaustion with $\geq 3/5$ criteria required to distinguish frailty.^{31,32} It is the most frequently cited tool shown to predict mortality and disability in large cohorts of community-dwelling elders and surgical patients.
 - Edmonton Frail Scale is an 11-item survey that assesses 8 dimensions of frailty. Each item is scored 0, 1, or 2 with higher scores indicating greater frailty. The total score ranges from 0-17 with good inter-rater reliability ($k = 0.77$), moderate internal consistency ($\alpha=0.62$), and strong correlation with a geriatrician's assessment of frailty ($r=.64$, $p<.001$).⁸⁸
 - Gait speed is one key measure of frailty^{76,97,98} that has excellent inter-rater reliability (intraclass coefficient 0.88-0.96) and test-retest reliability (intraclass coefficient 0.86-0.91).
 - Handgrip Strength has also been demonstrated to have key utility as an index of frailty.^{32,89} A grip dynamometer will be used, averaging 2 serial assessments from the dominant hand.
 - Prealbumin will be measured with standard serological testing. Changes can be detected in days, and it is the best available biomarker of nutrition.^{90,91} However, because

prealbumin can function as an acute phase reactant, we will also concurrently measure c-reactive protein as a measure of inflammation and interpret prealbumin as proposed by Jensen, et al.^{92,93}

- Body Mass Index (BMI) will be calculated from height and weight assessed each week at the Cardiac Rehab facility, and is considered the most suitable, objective anthropometric indicator of nutritional status,⁹⁴ and changes in BMI have been shown to predict survival in the elderly.⁹⁵
- Subjective Global Assessment of Nutrition (SGA) is the standard approach to nutritional assessment.⁹⁶ It evaluates multiple domains of nutrition and reliably categorizes patients into 1 of 4 categories: normal, mild-, moderate- and severely malnourished. We will use the 7-point SGA (See Appendix) because it is sensitive to 1-point changes in as little as 1 month and has excellent inter-rater reliability ($k=.726$).²⁸
